### **Outcomes {12}**

The primary outcome of interest is the following:

1. Household COVID-19 testing

Household COVID-19 testing uptake at the 9-month follow-up (9MFU) will be the primary outcome of interest. Our project will document testing uptake that is either administered by nurses or self-administered during home visits in the experimental arm, as well as self-reported information regarding COVID-19 testing uptake by study participants in the treatment and control groups. Participants will be asked whether they have received COVID-19 testing in the past three months, as well as about variables collected via the COVID-19 Symptoms, Diagnoses, and Testing scale. The COVID-19 Symptoms, Diagnoses, and Testing scale is adapted from the COVID-19 Cannabis Health Questionnaire. Specifically, participants will be asked questions regarding whether they are currently sick with an illness that might be related to COVID-19, any symptoms the participant experienced in the past three months, and the result of the participant's last COVID-19 test.

The secondary outcomes of interest are:

1. Household COVID-19 Testing Uptake

All medical services delivered by nurses during home-visits (such as COVID-19 test administration) will be carefully documented by the investigative team. At the time of the 6-month-follow-up (6MFU) assessment, the project team will obtain self-reported information regarding COVID-19 testing uptake by study participants in the treatment and control groups. Respondents will be asked whether they have received COVID-19 testing in the past six months. Respondents will also be asked questions from the COVID-19 Symptoms, Diagnoses, and Testing scale regarding whether they are currently sick with an illness that might be related to COVID-19, any symptoms the participant experienced in the past six months, and the result of the participant's last COVID-19 test.

2. COVID-19 control measure uptake

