### **Sample size {14}**

Power for the proposed study was calculated using Power Analysis and Sample Size software based on household level randomization, individual level outcomes using conservative estimates and adjusting for 15% attrition and allowing for subgroup analyses. A test for the difference in two proportions using a mixed model based on a clustered 3-Level Hierarchical Design with level-3 (household) 2:1 intervention: control randomization. The total sample size of 300, obtained from 100 level-3 units (households) in the intervention group and 50 level-3 units in the control group with an average of 2 level-2 units (individuals) per level-3 unit (household) and an average of 3 level-1 units (timepoints) per level-2 unit (individual), achieves >80% power to detect a difference between the group proportions of at least 0.15. The proportion in group 2 is 0.10. The correlation of level-1 units within a level-2 unit is <0.7. The correlation of level-2 units within a level-3 unit is <0.3. A test based on a mixed-effects logistic regression is anticipated at a significance level of 0.05.

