#### **Plans to promote participant retention and complete follow-up {18b}**

During the consent process, the study team will obtain extensive tracking information, including phone numbers, email addresses, and home addresses. Participants will be asked to provide contact information for three people who know how to reach them in most circumstances. These methods were used in previous work in the South Bronx with an attrition rate of 8% over 12 months [17]. Prior experience indicates that virtually all respondents will have a cell phone or access to a phone. However, as part of the consent process, we will obtain permission to revisit the home to make follow-up appointments if phone contact is not possible. Additionally, we will allow for flexibility in scheduling by conducting reminder calls before scheduled data collection appointments.

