A Nurse-Community Health Worker-Family Partnership Model: Addressing Uptake of COVID-19 Testing and Control Measures

Statistical Analysis Plan (SAP)

Unique Protocol ID: 3P30DA011041-23S1

Protocol Version: 1.1

NCT #: NCT04832919

Document Date: 07/12/22

Contributors:

[name] – Senior Biostatistician

[name] – Junior Research Scientist/Data Manager

STATISTICAL DESIGN AND POWER

Measures.

Definition of Primary Outcomes

Household COVID testing uptake at the 9-month follow up is one of the main primary outcomes of interest. The investigative team will document all medical services administered by nurses during home visits, as well as self-reported information regarding COVID-19 testing uptake by study participants in the treatment and control groups. Participants will be asked whether they have received COVID-19 testing in the past three months [Yes/No]. Additionally, variables collected via the COVID-19 Symptoms, Diagnoses, and Testing Scale are the primary outcomes. This questionnaire is adapted from the COVID-19 Cannabis Health Questionnaire (CCHQ) (Vidot et al, 2020) and will measure COVID-19 symptoms, diagnoses, and testing. At the 9-month follow up point, participants will be asked questions regarding whether they are currently sick with an illness that might be related to COVID-19, any symptoms the participant experienced in the past three months [Check All That Apply], and the result of the participant's last COVID-19 test [Positive/Negative].

Definition of Secondary Outcomes

For the randomized trial, data collected utilizing the following questionnaires are secondary outcomes:

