There are several mediating variables of interest including: knowledge and self-efficacy for COVID-19 prevention, testing salience, habitual processes, and medical mistrust. These measures are captured in the baseline, 6-month, and 9-month questionnaires. **Figure 2** features all mediating variables considered for these analyses.

Created Variables

We will create summary scores for all survey scales using validated scoring procedures. We will create difference variables (e.g., 6 month-baseline, 9 month – 6 month, 9 month-baseline) for time varying variables (e.g., vaccination status, COVID-19 exposure, employment status) measured at multiple time points.

Figure 1: Consort Flow Diagram

[figure not shown]
[figure not shown]

Figure 2: NCFP Theoretical Model

Design.

The randomized control trial will include 150 households, and 400 individual household members who will be randomized into 2 arms with parallel assignment in a 2:1 ratio, intervention:control. Participants in the intervention arm will receive the Nurse-Community Health Worker-Family Partnership intervention. The control arm will receive standard access to NYC Department of Health COVID-19 testing sites and standard COVID-19 public health messaging for NYCHA residents.

Framework.

With regard to hypothesis testing, the trial will utilize a superiority hypothesis testing framework. The study team will compare differences between baseline data and data collected at the 9-month follow-up timepoint to assess whether or not the intervention group had a higher efficacy in regards to the outcomes of interest than that of the control group.

Randomization.

After the baseline assessment and confirmation of eligibility, treatment allocation will be determined using a household-level randomization scheme of 2:1. The study team will randomize households using the password-protected REDCap desktop app using a predetermined randomization algorithm entered into the EDC system.

Interim Analyses.

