across 3 racial/ethnic groups (White, Black, Hispanic). These differences will be examined in bivariate analyses (unadjusted) and multivariable analysis (adjusted). We will develop multilevel multivariable regression models to examine the association between predictors, mediators, and moderators on the primary outcome (testing uptake) and secondary outcomes (COVID mitigation practices, and family mutual aid). We will use multivariable multilevel logistic (binary outcomes) and linear (continuous outcomes) regression models to conduct cross-sectional analysis at each time point. For outcomes where statistical distributional assumptions are violated we will use the *non-parametric multilevel mixture model (NPMM)*. In this model, latent classes are extracted at multiple levels of a hierarchical data structure (e.g., individual, household) and, unlike the conventional multilevel models (MLM), there are no continuously distributed random effects.^{1,2}

Longitudinal Analysis

We will use a random-intercepts logistic (with a binary response) or linear (continuous outcome) multilevel regression model, for each timepoint t , individual i , that is a member of household j . A random-intercepts model will give the conditional assessment of the extent to which household-level exposures vary on the outcomes after taking into account individual-level exposures, assuming the household-level variation is normally and independently distributed with a constant variance. The variance partitioning coefficient (VPC), or the amount of variability in the outcome attributed to predictors at each level, will be calculated. This will tell us to which extent household level and individual-level variables contribute to the outcome allowing for an examination of the impacts of COVID-19 at multiple levels. Structural equation models (SEM) will be used to examine mediating and moderating variables in the regression analyses. In addition, we will conduct sensitivity analyses (e.g., intent to treat vs receive intervention, components of intervention received, per protocol) and subgroup analyses (e.g., race/ethnicity, gender, age, education, essential worker) based on findings from aims 1-3.

For binary outcomes, we will use a random-intercepts logistic multilevel regression model, for each timepoint t , individual i , that is a member of household j . The basic equation will follow the form:

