Consensus has yet to be determined on the precise power calculations for multilevel models[1-3]. Subramanian and other respected scholars in multilevel modeling argue that if the purpose of the multilevel model is to estimate the variation of level-1 variables, the size of the level-1 variable is really the driving factor [2,3]. Power for the proposed study was calculated using Power Analysis and Sample Size software (PASS 2020) based on household level randomization, individual level outcomes using conservative estimates and adjusting for 15% attrition and allowing for subgroup analyses [4]. A test for the difference in two proportions using a mixed model based on a clustered 3-Level Hierarchical Design with level-3 (household) 2:1 intervention: control randomization. The total sample size of 300, obtained from 100 level-3 units (households) in the intervention group and 50 level-3 units in the control group with an average of 2 level-2 units (individuals) per level-3 unit (household) and an average of 3 level-1 units (timepoints) per level-2 unit (individual), achieves >80% power to detect a difference between the group proportions of at least 0.15. The proportion in group 2 is 0.10. The correlation of level-1 units within a level-2 unit is <0.7. The correlation of level-2 units within a level-3 unit is <0.3. A test based on a mixed-effects logistic regression is anticipated at a significance level of 0.05.

References:

2. Snijders AT. Power and sample size in multilevel modeling. 2005;3:1570-1573.
3. NCSS LLC. PASS 2020 Power Analysis and Sample Size Software; 2020. ncss.com/software/pass.
6. Robinson TJ. Multilevel Analysis: Techniques and Applications. *J Am Stat Assoc*. 2003;98(462):496-496.
7. Hox JJ. Multilevel Analysis: Techniques and Applications. Psychology Press; 2002.
8. Joreskog, K. G., & Sorbom D. (1988). PRELIS: A Program for Multivariate Data Screening and Data Summarization. A Preprocessor for LISREL. Chicago: SSI, Inc.
9. Joreskog, K. G. (1978). Structural analysis of covariance and correlation matrices. *Psychometrika*, 43, 443-477.

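### The >80% power is for a three-timepoint test: the 9-month primary outcome has no stated power and no named confirmatory analysis, and the subgroup allowance is unsupported

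*SAP*

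**What the plan says.** **Power.** The SAP (Power and Sample Size) and the Protocol (Sample size {14}) carry the same calculation. It assumes 100 intervention and 50 control households, 2 people per household, a control proportion of 0.10, a within-person correlation below 0.7, a within-household correlation below 0.3, and a 0.05 level. The key statement is "an average of 3 level-1 units (timepoints) per level-2 unit (individual), achieves >80% power to detect a difference between the group proportions", where the difference is 0.15 or larger. It is introduced as using "conservative estimates and adjusting for 15% attrition and allowing for subgroup analyses". Which three timepoints are meant is not stated.

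**Primary outcome.** Protocol, Outcomes {12}: "Household COVID-19 testing uptake at the 9-month follow-up (9MFU) will be the primary outcome of interest". SAP, Definition of Primary Outcomes: "Household COVID testing uptake at the 9-month follow up is one of the main primary outcomes of interest". The SAP then also makes the variables of the symptoms, diagnoses and testing scale primary. SAP, Final Analysis, nevertheless justifies having no multiplicity adjustment by the clarity of the primary outcome.

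**Analysis.** SAP, Framework, says the team will "compare differences between baseline data and data collected at the 9-month follow-up timepoint". SAP, Analysis for Aim 4, plans multilevel "regression models to conduct cross-sectional analysis at each time point". SAP, Longitudinal Analysis, adds a three-level mixed-model test of two proportions. None is labelled primary or confirmatory. The model equation lists vectors of time-varying, individual and household covariates, with no explicit arm contrast at 9 months.

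**Counts.** SAP, Design: "The randomized control trial will include 150 households, and 400 individual household members", against 300 people in the power text. Protocol, Trial design {8}, gives the control group as 150, beside 150 households in all, a 2:1 ratio and 100 in the intervention group.

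**The concern.** The one power figure belongs to a test that uses three observations per person, while the outcome on which the trial is to be judged is one yes/no answer per person at 9 months. A null 9-month result, or a null subgroup result, would be read against a >80% that was calculated for a different test and for the whole sample. Because no analysis is named confirmatory and the SAP has more than one primary variable, the result that counts could be chosen after the data are seen, with no multiplicity adjustment to limit this.

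**Working it through.** **Inputs.** All come from the sample-size text: proportions 0.25 and 0.10, 100 and 50 households, m2 = 2 people per household, m1 = 3 timepoints, and correlations at their limits, r1 = 0.7 within person and r2 = 0.3 within household. The two-sided 0.05 level is from SAP, Final Analysis.

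**Formulas.** Design factor f = 1 + (m1 − 1)·r1 + m1·(m2 − 1)·r2. Effective n per arm = households × m1 × m2 / f. With s1² = 0.1875/n1 + 0.09/n2 and s0² = 0.20 × 0.80 × (1/n1 + 1/n2):
- unpooled power = Φ(0.15/s1 − 1.96)
- pooled power = Φ((0.15 − 1.96·s0)/s1)
- logistic Wald power uses the log odds ratio, ln 3 = 1.099, and its standard error.

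**Step 1: reproduce the plan's figure.** f = 1 + 1.4 + 0.9 = 3.3. Effective n = 600/3.3 = 181.8 and 300/3.3 = 90.9. Then s1 = 0.0450 and s0 = 0.0514, and pooled power = Φ((0.15 − 0.1007)/0.0450) = 86.4%. Unpooled gives 91.6% and Wald 80.6%. All exceed 80%, so the figure stands for the test described.

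**Step 2: one 9-month value per person.** f = 1 + 0.3 = 1.3. Effective n = 200/1.3 = 153.8 and 100/1.3 = 76.9.

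| 300 people, r2 = 0.3 | Unpooled | Pooled | Wald |
|---|---|---|---|
| Three timepoints, no loss | 91.6% | 86.4% | 80.6% |
| One timepoint, no loss | 86.6% | 79.6% | 73.8% |
| Three timepoints, 15% of households lost | 86.8% | 79.8% | 73.9% |
| One timepoint, 15% of households lost | 80.8% | 72.2% | 66.8% |

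Within a formula and loss pattern, the change of timepoints costs 5.0 to 7.6 points.

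**Step 3: what else moves the 9-month figure** (pooled).
- 15% of individuals lost instead of households: f = 1.21, 75.6%.
- r2 = 0.1: f = 1.1, effective n 181.8 and 90.9, the same as in step 1; 86.4% with no loss and 79.8% after household loss.
- 400 people (2.667 per household), r2 = 0.3: f = 1.5, 85.5% and 78.9%.
- Household loss of 8%, from Protocol {18b}, which cites previous work "with an attrition rate of 8% over 12 months": 75.9% with 300 people and 82.2% with 400 (r2 = 0.3).

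**Step 4: attrition.** Pooled 80% power for the three-timepoint test needs 128.0 households, and 128.0/0.85 = 150.5, which fits 150. The other reading is that 300 is the head count after attrition, so that 300/0.85 = 353 would be enrolled. The text does not say which applies.

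**Step 5: subgroups.** The documents give no subgroup size; half the sample is my assumption, with no loss.

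| Half-sample | Unpooled | Pooled | Wald |
|---|---|---|---|
| Half the households, 9 months | 58.3% | 47.2% | 45.0% |
| Half the households, three timepoints | 65.5% | 54.7% | 51.4% |
| One member per household, 9 months | 69.7% | 59.3% | 55.3% |
| One member per household, three timepoints | 79.0% | 70.1% | 64.8% |

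These use the stated 300 people and correlation limits, and none reaches 80%. Half of 400 people with no clustering at all gives 81.5/73.1/67.6% at 9 months, but that drops the stated household correlation.

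**The case against.** **The powered test is a planned test.** SAP, Longitudinal Analysis, describes the same three-level test as the power text. This stands, and it is why the figure is not an error. But that test is neither called primary nor tied to 9 months.

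**The analyses are not real rivals.** The SAP orders them as cross-sectional first and longitudinal second. The three-level model could supply the baseline-to-9-month contrast, and Protocol {20c} fixes intent-to-treat for reporting. This largely stands: the gap is a missing label and a missing explicit contrast, not three competing plans.

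**The trial may be adequately powered.** The correlations are given as upper limits, and the figures above are unadjusted. A change-from-baseline comparison could reach roughly 85% to 98%, but on inputs the documents do not give: baseline uptake of 10% in both arms, within-person correlation 0.5 to 0.7, design factor 1.3. A reader might infer that the 9-month analysis is underpowered; the documents do not show that. Nor does the mismatch put power anywhere from 67% to 96%, the range over all formulas, loss patterns, correlations and head counts tried. Most of that spread comes from those choices, not from the timepoints.

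**Attrition is allowed for.** This stands. A reader might infer that the 15% was never built in, but 150 households is consistent with it. Only the working is missing.

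**400 may be planned enrolment and 300 the cautious basis.** This is possible (400 × 0.85 = 340), so the two numbers are unreconciled, not proven contradictory.

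**Subgroups are contingent on earlier aims, and no text claims >80% for them.** Both are true, but the sample-size text still says the size allows for them and gives nothing to support it.

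**Conclusion.** The concern holds in a limited form and should be fixed. The stated >80% is correct for a three-timepoint test but is not the power of the 9-month primary outcome, for which none is given. At r2 = 0.3 with 300 people, the difference is about 5 to 8 points of unadjusted power. Whether this crosses 80% depends on the formula, the correlation, the loss and the head count.

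Two statements are not supported as written. The subgroup allowance fails at the stated correlation limits (about 47% and 55%, pooled, for an assumed half of the households). The control group of 150 in Protocol {8} conflicts with that section's own totals, which leave 50.

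The SAP's several primary variables do not fit its reason for omitting a multiplicity adjustment. All power figures take the 0.10 and 0.25 proportions as given and use average household size.

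**What to change.** 1. In the SAP, make 9-month testing uptake the single primary outcome, as in Protocol {12}. Name as confirmatory its arm contrast in a multilevel logistic model with a household random effect, adjusted for baseline testing. Label the other models supportive. Check which baseline item will serve: SAP Aim 1 describes whether a person has ever been tested, while the 9-month question covers the past three months.
2. Restate power for one 9-month observation per person, with and without 15% attrition, over household correlations of 0.1 to 0.3. Name the formula, and note that baseline adjustment may raise the figure.
3. Delete the subgroup clause from both sample-size texts and label subgroup analyses exploratory.
4. Correct the control group in Protocol {8} from 150 to 50 households.
5. State whether 300 people and 150 households are before or after attrition, and reconcile 300 with the 400 in SAP, Design.

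The cost is text only: no extra participants, visits or data. The stated power may become less favourable. Because the SAP plans six-monthly interim reviews that include study outcomes, the amendment should record whether outcomes by arm had been seen when it was made.

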The data team will conduct interim analyses every 6 months during the duration of the trial. The analysis will review data on recruitment, participant characteristics, protocol compliance, and study outcome. This analysis will also assess the differential proportion of self-reported COVID-19 infection between the two treatment groups (a safety assessment of the trial primary outcome). There are no planned adjustments of the significance level due to interim analysis. In addition, cross-sectional analyses will be completed after data collection for each time point (baseline, 6-month, 9-months).

Final Analysis.

The final analysis will be conducted once outcome data for all enrolled participants is collected, outside of participants who withdrew early or were lost to follow-up. If the trial is not stopped early for any reason, the final analysis will be conducted using available data. Since the primary outcome is clearly defined, the level of

significance of this study will not be adjusted for multiplicity. All hypothesis tests will be 2 sided, with a 95% confidence interval.

Trial Population.

Inclusion Criteria

- Residence in one of the NYCHA complexes in Mott Haven, South Bronx
- English or Spanish-speaking
- Age 10 years or older
- Willing and able to provide informed consent or assent

Exclusion Criteria

- Non-resident of one of the NYCHA complexes in Mott Haven, South Bronx
- Does not speak English nor Spanish
- Younger than 10 years old, unless household index case tests antigen positive. In this instance, all members of family will be included.
- Unwilling or unable to provide informed consent or assent

Screening Data

Screening data will be summarized on a quarterly basis during the recruitment period, as well as in final reports, those invited to participate in the study will be classified as eligible or ineligible in order to describe the representativeness of the study population.

Withdrawal/Follow Up

The team expects a low level of attrition from withdrawal or loss to follow-up from the study due to the infrequency of study assessments, the community engaged research approaches used in the intervention, the average length of residency in NYCHA housing, and the duration of the follow up period. Withdrawal and lost to follow up data will be reported with the 6-month and 9-month follow up data. Demographic characteristics of participants who withdraw or are loss to follow-up will be examined and compared to those who complete the study.

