Adherence to Study Protocol

For the purposes of this project, study adherence is defined as the participants completion of all study related activities (intervention visits, questionnaires). Field workers will routinely contact participants and alert the study team if a participant is unable to be reached. The data monitoring team will routinely produce reports to track participant status and compliance with protocol specified assessments and visits.

Protocol Deviations

All protocol deviations will be documented by the study team. A protocol deviation will be defined as any missed, or out-of-window study assessment, as well as randomization of a participant who is not eligible at baseline. All protocol deviations will be reported during routine data status reports, as well as to the IRB (as required).

Harms

There are no anticipated harms for this trial. All unexpected adverse events and serious adverse events will be captured in detail by the study team, as well as their severity, expectedness, and causality.

Statistical Methods.

SAS, M Plus, R, and/or Stata statistical software will be used for data analysis; statistical significance will be assessed as $p < 0.05$. For the RCT we will conduct analysis in two stages, starting with cross-sectional analysis at each time point and subsequently conducting longitudinal analysis.

Baseline Participant Characteristics

We will analyze demographic variables such as age, biological sex, gender identity, sexual identity, race, ethnicity, language preference, body measurements, and several socioeconomic measures collected via

questions adapted from the General Social Survey (GSS) 2014. Initial descriptive analyses will include an examination of the sample characteristics at each level (participants, households) at each of the time points for the randomized controlled trial (baseline, 6 months, 9 months). Continuous variables will be summarized using the mean, standard deviation, median, range, and interquartile range, while nominal and ordinal variables will be summarized using frequencies and percentages.

Aim 1 is to describe self-reported baseline rates of SARS-CoV2 diagnostic testing (PCR and antibody), receipt of results, illness, hospitalization and severe disease.

Analysis for Aim 1

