Aim 4 is to (With our community advisors) develop, implement and test the effectiveness of a Nurse-Community Health Worker-Family Partnership intervention to increase reach, acceptance and uptake of diagnostic testing, adherence to COVID-19 prevention strategies, and development of a household mutual aid strategy to respond to COVID-19 related events within the home and community.

Analysis for Aim 4

The analysis for Aim 4 will encompass all variables of interest in Aims 1, 2, and 3 collected at baseline, six months, and nine months. Descriptive analyses will include participant and household level testing uptake, adherence to public health mitigation strategies, and household cohesion at each of the time points for the randomized controlled trial. Data will be stratified with respect to important demographic factors (e.g., age, race, gender, ethnicity). Continuous variables will be summarized using the mean, standard deviation, median, range, and interquartile range, while nominal and ordinal variables will be summarized using frequencies and percentages. Bivariate analyses will be conducted to examine associations between the outcomes of interest (testing uptake, COVID mitigation practices, and household mutual aid) and key predictors (intervention group), confounders (previous infection or vaccination), moderators (e.g., gender, age, testing fatigue), and demographic characteristics. To examine bivariate associations between continuous variables that are approximately normal or may become approximately normal after an appropriate transformation, the Student's t-test will be used. For other continuous variables where normality cannot be assumed, the Wilcoxon rank-sum test will be used instead. Chi-square tests will be used to assess group differences for nominal data. We will use Chi-square tests and the Cochran Mantel-Haenszel tests for comparison in ordinal characteristics. The Fisher's exact test will be considered for contingency tables with sparse cells. We will compare outcomes

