$$y_{tij} = \ln\left(\frac{\pi_{tij}}{1 - \pi_{tij}}\right) = B_0x_{0ij} + \beta_1x_{tij} + \beta_2x_{ij} + \beta_3x_j + \varepsilon_{i(j)}^{(2)} + \varepsilon_j^{(3)}$$

For continuous outcomes, we will use a random-intercepts multilevel regression model, for each timepoint t , individual i , that is a member of household j . The basic equation will follow the form:

$$y_{tij} = B_0x_{0ij} + \beta_1x_{tij} + \beta_2x_{ij} + \beta_3x_j + \varepsilon_{i(j)}^{(2)} + \varepsilon_j^{(3)}$$

A random-intercepts model will give the conditional assessment of the extent to which household-level exposures vary on the outcomes after taking into account individual-level exposures, assuming the household-level variation is normally and independently distributed with a constant variance. Where y_{tij} represents the outcome for the i^{th} individual that resides in household j and time t , x_{tij} denotes the vector of time-varying covariates (e.g., exposure to COVID-19, household member exposed, household member infected), x_{ik} denotes the vector of individual-level variables (e.g., age, gender, race, ethnicity, comorbidities), and x_k is a vector of household-level variables (e.g., household plan developed). The vector of regression coefficients for the time-varying variables is denoted as β_1 ; similarly, β_2 denotes the vector of regression coefficients for the individual-level variables, and β_3 denotes the vector of regression coefficients for the household-level variables.

The random effect for individual i that is a member of household j is denoted by $\varepsilon_{i(j)}^{(2)}$, and $\varepsilon_j^{(3)}$ denotes the random effect for the third (household-level) cluster. We assume the random effects are independent and normally distributed [5-7]. The variance partitioning coefficient (VPC), or the amount of variability in the outcome attributed to predictors at each level, will be calculated. This will tell us to which extent household level and individual-level variables contribute to the outcome allowing for an examination of the impacts of COVID-19 at multiple levels. In order to examine these impacts, a test for the difference in two proportions using a mixed-effects regression model based on a clustered 3-Level Hierarchical Design with level-3 (household) randomization will be utilized.

Mediation, moderation, and mediated moderation, moderated mediation analyses

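### On the natural reading of the SAP, baseline is one of the three timepoints in the powered between-arm test; this dilutes a 0.15 difference to about 0.10 and takes power below the stated >80%

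*SAP*

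**What the plan says.** **Power.** The SAP (Power and Sample Size) assumes 100 intervention and 50 control households, 2 people per household and 3 timepoints per person. It states the result thus: "average of 3 level-1 units (timepoints) per level-2 unit (individual), achieves >80% power to detect a difference between the group proportions". That difference is set at 0.15 or more, with 0.10 in the control arm. Protocol, Sample size {14}, has the same sentence, including "an average of 3 level-1 units (timepoints) per level-2 unit (individual". Neither names the three timepoints.

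**Timepoints.** The SAP (Baseline Participant Characteristics) describes the sample "at each of the time points for the randomized controlled trial (baseline, 6 months, 9 months". Its Interim Analyses section lists the same three. The efficacy analysis, Aim 4, "will encompass all variables of interest in Aims 1, 2, and 3 collected at baseline, six months, and nine months".

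**Test.** The Longitudinal Analysis section writes a random-intercepts model for timepoint, person and household. No arm, time or arm-by-time term appears in it. It closes with "a test for the difference in two proportions using a mixed-effects regression model based on a clustered 3-Level Hierarchical Design with level-3 (household) randomization", which is close to the wording of the power section.

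**Start of intervention.** The SAP (Randomization) places allocation after the baseline assessment. In Protocol, Implementation {16c}, the intervention team learns of a household only once baseline is complete.

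**Primary outcome.** Both documents set it at 9 months, with three-month recall. Testing at 6 months, with six-month recall, is secondary.

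**The concern.** The power calculation credits every one of the three occasions with a difference of 0.15. If one of them is baseline, the true difference there is zero by design, and a single arm effect fitted over all three averages that zero in. An intervention working exactly as planned would then show a difference about one third too small, and at the correlation ceilings it would be missed in roughly four trials in ten or more. This can be avoided with the same households and the same data.

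**Working it through.** **Inputs.** Control proportion 0.10 and difference 0.15, so 0.25 in the intervention arm; 100 and 50 households; K = 2 people per household; M = 3 timepoints; correlation ceilings ρ1 = 0.7 (within person) and ρ2 = 0.3 (within household); 15% attrition. All are from the SAP, Power and Sample Size. The level is from the same section ("A test based on a mixed-effects logistic regression is anticipated at a significance level of 0.05") and the sidedness from Final Analysis ("All hypothesis tests will be 2 sided, with a 95% confidence interval").

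**Formulae.**
- Design effect: DE = 1 + (M − 1)ρ1 + M(K − 1)ρ2
- Effective n per arm = households × K × M / DE
- Power, unpooled variance: Φ(d/SE1 − 1.96)
- Power, pooled variance: Φ((d − 1.96·SE0)/SE1)

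Here d is the difference, SE1 the standard error under the alternative and SE0 the standard error under the null. Ranges run from pooled to unpooled. For 15% loss, effective n is multiplied by 0.85 with DE unchanged.

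**Step 1: reproduce the plan's figure.**
- DE = 1 + 2(0.7) + 3(1)(0.3) = 3.30.
- Effective n = 600/3.30 = 181.8 and 300/3.30 = 90.9.
- SE1 = √(0.25·0.75/181.8 + 0.10·0.90/90.9) = 0.0450. Mean proportion 0.20, so SE0 = √(0.16(1/181.8 + 1/90.9)) = 0.0514.
- Power = 86.4% pooled, 91.6% unpooled; after 15% loss, 79.8% and 86.8%.

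The stated >80% reproduces, apart from the marginal 79.8%.

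**Step 2: let one of the three occasions be baseline.** Assume equal weights, 0.10 in both arms at baseline, and 0.25 v 0.10 at months 6 and 9.
- Difference = (0 + 0.15 + 0.15)/3 = 0.10, that is 0.20 v 0.10.
- DE is still 3.30. SE1 = √(0.20·0.80/181.8 + 0.10·0.90/90.9) = 0.0432. Mean proportion 0.167, so SE0 = 0.0479.
- Power = 55.7% pooled, 63.8% unpooled; after 15% loss, 48.5% and 56.8%.

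**Step 3: vary the correlations.** The plan gives them only as upper bounds. The lower pairs are assumptions.

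| ρ1 / ρ2 | DE | Power, baseline pooled | After 15% loss |
|---|---|---|---|
| 0.7 / 0.3 | 3.3 | 56–64% | 49–57% |
| 0.5 / 0.2 | 2.6 | 67–74% | 59–67% |
| 0.3 / 0.1 | 1.9 | 81–86% | 74–80% |

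SAP, Design, gives 400 individuals, not 300. With K = 400/150 at 0.7/0.3, DE = 3.90 and pooled-baseline power is 61–69% before loss.

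**Step 4: tests that leave baseline out of the outcome** (0.25 v 0.10, at 0.7/0.3).

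| Outcome occasions | DE | Effective n | Power | After 15% loss |
|---|---|---|---|---|
| Months 6 and 9 averaged (M = 2) | 2.3 | 173.9 / 87.0 | 85–90% | 78–85% |
| Month 9 only (M = 1) | 1.3 | 153.8 / 76.9 | 80–87% | 72–81% |

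The month-9 lower figure is 79.7% before rounding. Neither row includes any gain from adjusting for baseline.

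**Step 5: cross-check.** Correlated binary data were simulated at the ceilings and analysed by household means, a simpler test than the planned mixed-effects logistic regression. Power was 66% with baseline pooled (60% after loss), against 89% (84%) with 0.15 at all three occasions and 85% (80%) for month 9 alone. The simulated loss is somewhat smaller than the formula's, but the conclusion is the same.

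**The case against.** The strongest reply is that pooling over baseline is an inference.

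- The power section does not name its three timepoints, and the model equation never shows where treatment arm enters. An arm-by-time term, or an exposure coded zero at baseline, is not excluded.
- SAP, Framework, describes a baseline-to-9-month comparison, and Created Variables plans difference scores. Analysis for Aim 4 plans separate models at each timepoint. Baseline dilutes none of these. In the simulation a 9-month-minus-baseline change had about 99% power at the ceilings, where high within-person correlation favours it.
- The Protocol collects data at eight timepoints, so the set of three cannot be read into its copy of the power sentence.

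All of this stands. A reader might infer that the SAP certainly pools baseline, or that >80% is an arithmetic error. The documents support neither: the pooling is nowhere stated, and the figure follows from its own inputs.

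The size of the loss also depends on assumptions: equal weights, the full effect already present at month 6, and a baseline proportion of 0.10, which is given nowhere. The correlations are ceilings. The SAP says its calculation already adjusts for 15% attrition, so the after-loss figures may count it twice; the before-loss figures do not depend on that.

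The reply does not remove the problem. The undiluted comparisons are not the three-timepoint test that the power section describes, and nothing says which test is confirmatory. The test that does match the powered design is the one in Longitudinal Analysis, and nothing there separates occasions before and after randomisation.

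**Conclusion.** The point holds in conditional form. On the SAP's natural reading, the three powered timepoints are baseline, 6 and 9 months, and a single arm difference over them includes an occasion with no possible effect. Under the assumptions in step 2, the tested difference falls from 0.15 to about 0.10. Power is then about 56–64% at the stated ceilings (49–57% if 15% are lost) and 67–74% at 0.5/0.2, and it reaches 80% only near 0.3/0.1. The SAP calls its inputs conservative, so the ceilings are a fair reference.

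This does not show that the trial is underpowered under every analysis the SAP mentions. It shows that the stated power cannot be relied on until the plan says which occasions are outcomes, how baseline enters, and which contrast is confirmatory.

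**What to change.** **SAP, Longitudinal Analysis.** Write treatment arm, time and arm-by-time into the model. Use only post-randomisation occasions as outcomes in the between-arm test, and enter baseline testing as a covariate. Name the arm contrast at 9 months as confirmatory, because that is the primary outcome. An average over months 6 and 9 can be reported in addition, but should not replace it: it would merge the primary outcome with a secondary one that has a different recall period.

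**SAP, Power and Sample Size, and Protocol, Sample size {14}.** Name the timepoints, say whether the 300 individuals are before or after attrition, and restate power at 0.7/0.3 as a range by variance formula:
- 9 months alone: about 80–87% (72–81% after 15% loss).
- Months 6 and 9 averaged, if reported: about 85–90% (78–85%).

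State that these figures take no credit for baseline adjustment.

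**Cost.** Wording in two documents and one re-run of the power calculation, with no new participants or data. The one drawback is a slightly less favourable stated power: the lower 9-month figure is just under 80% even before loss.
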